7.1 Adverse events

An adverse event (AE) is any untoward medical occurrence (e.g., any unfavorable and unintended sign [including abnormal laboratory findings], symptom or disease) in a subject or clinical investigation subject *after providing written informed consent* for participation in the study until the end of study visit. Therefore, an AE may or may not be temporally or causally associated with the use of a medicinal (investigational) product. Medical conditions/ diseases

present before first intake of study drug are only considered adverse events if they worsen after study start.

In addition, all reports of intentional misuse and abuse of the product are also considered an adverse event irrespective if a clinical event has occurred.

The occurrence of adverse events must be sought by non-directive questioning of the patient at each visit during the study. Adverse events also may be detected when they are volunteered by the patient during or between visits or through physical examination findings, laboratory test findings, or other assessments.

Abnormal laboratory values or test results constitute adverse events only if they fulfill at least one of the following criteria:

- they induce clinical signs or symptoms,
- they are considered clinically significant,
- they require therapy.

Clinically significant abnormal laboratory values or test results must be identified through a review of values outside of normal ranges/clinically notable ranges, significant changes from baseline or the previous visit, or values which are considered to be non-typical in patient with underlying disease. Investigators have the responsibility for managing the safety of individual patient and identifying adverse events. Alert ranges for laboratory and other test abnormalities are included in Appendix 1. Clinically significant abnormal laboratory values will also be assessed for the following parameters of the biomarker sub-study (only for patients participating in the biomarker sub-study): Adiponectin, leptin, insulin, HOMA-IR, proinsulin, IL-6, TNF-alpha, M30 assay, NT-proBNP.

Adverse events must be recorded in the Adverse Events CRF under the signs, symptoms or diagnosis associated with them, accompanied by the following information:

- the severity grade
 - mild: usually transient in nature and generally not interfering with normal activities
 - moderate: sufficiently discomforting to interfere with normal activities
 - severe: prevents normal activities

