7.3 Liver safety monitoring

To ensure patient safety and enhance reliability in determining the hepatotoxic potential of an investigational drug, a standardized process for identification, monitoring and evaluation of liver events has to be followed.

The following two categories of abnormalities / adverse events have to be considered during the course of the study (irrespective of whether classified/reported as (S)AE):

- Liver laboratory triggers, which will require repeated assessments of the abnormal laboratory parameter
- Liver events, which will require close observation, follow-up monitoring and completion of the standard base liver CRF pages

Please refer to Table 14-1 in Appendix 2 for complete definitions of liver laboratory triggers and liver events.

Every liver laboratory trigger or liver event as defined in Table 14-1 of Appendix 2 should be followed up by the investigator or designated personal at the trial site as summarized below. Detailed information is outlined in Table 14-2 in Appendix 2.

For the liver laboratory trigger:

- Repeating the liver function test (LFT) within the next week to confirm elevation.

These LFT repeats must be performed using the central laboratory if possible. If this is not possible, then the repeats can be performed at a local laboratory to monitor the safety of the patient. Repeats laboratory must then be performed at central laboratory as soon as possible. If a liver event is subsequently reported, any local LFTs previously conducted that are associated with this event must be reported on the Liver CRF pages.

- If the elevation is confirmed, close observation of the patient will be initiated, including consideration of treatment interruption if deemed appropriate.

For the liver events:

- Repeating the LFT to confirm elevation as appropriate
- Discontinuation of the investigational drug if appropriate
- Hospitalization of the patient if appropriate
- A causality assessment of the liver event via exclusion of alternative causes (e.g., disease, co-medications)
- An investigation of the liver event which needs to be followed until resolution.

These investigations can include serology tests, imaging and pathology assessments, hepatologist's consultancy, based on investigator's discretion. All follow-up information, and the procedures performed must be recorded on appropriate CRF pages, including the liver event overview CRF pages.

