

Shoelson SE, Goldfine AB (2009) Getting away from glucose: fanning the flames of obesity-induced inflammation. *Nat Med*; 15:373-4

Takahashi H, Izuka H (2012) Psoriasis and metabolic syndrome. *J Dermatol*; 39:212-8

13 **Appendix 1: Clinically notable laboratory values and vital signs**

The following criteria will be used to define expanded limits and notable abnormalities of key laboratory tests. Notable values for blood pressure and pulse are presented in section **Error! Reference source not found.**

No specific action is pre-defined within this protocol to respond to specific abnormal laboratory values except for the follow up requirement for liver events as specified in Appendix 2, as it will be decided by the investigator/qualified site staff whether and which specific action needs to be taken to respond to any abnormal values, taking into account the overall status of the subject.

Liver Function and Related Variables

| | |
|-----------------------|-----------------------------------|
| ALT (SGPT): | > 3 x Upper Limit of Normal (ULN) |
| AST (SGOT): | > 3 x ULN |
| Total bilirubin: | > 1.5 x ULN |
| Alkaline phosphatase: | > 2 x ULN |

Renal Function and Electrolyte Variables

Creatinine (serum): $> 1.5 \times \text{ULN}$

Hematology Variables

Hemoglobin: $\geq 20 \text{ g/dL}$ decrease from baseline

Platelet count: $< \text{Lower Limit of Normal (LLN)}$

White blood cell count: $< 0.8 \times \text{LLN}$

Neutrophils: $< 0.9 \times \text{LLN}$

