Eosinophils: $> 1.1 \times \text{ULN}$

Lymphocytes: $> 1.1 \times \text{ULN}$

14 Appendix 2: Liver event definitions and follow-up requirements

Table 14.1 Liver Event Definitions

| | Definition/ threshold |
|--|--|
| Adverse event of special interest | |
| Laboratory values | ALT or AST $> 3 \times \text{ULN}$ ALP $> 2 \times \text{ULN}$ TBL $> 1.5 \times \text{ULN}$ |
| Medically significant event (SAE) | |
| Laboratory values | ALT or AST $> 5 \times \text{ULN}$ (with or without TBL $> 2 \times \text{ULN}$ [mainly conjugated fraction]) ALP $> 5 \times \text{ULN}$ (with or without TBL $> 2 \times \text{ULN}$ [mainly conjugated fraction]) TBL $> 3 \times \text{ULN}$ Potential Hy's Law cases (defined as ALT/AST $> 3 \times \text{ULN}$ and TBL $> 2 \times \text{ULN}$ [mainly conjugated fraction] without notable increase in ALP to $> 2 \times \text{ULN}$) |
| Adverse events | Any clinical event of jaundice (or equivalent term) ALT or AST $> 3 \times \text{ULN}$ accompanied by general malaise, fatigue, abdominal pain, nausea, or vomiting, or rash with eosinophilia Any event that links to a preferred term (PT) in the MedDRA dictionary falling under the SMQ sub-module "Drug-related hepatic disorders – severe events only"* or any "Hy's law case" PT |

* These events cover the following: hepatic failure, fibrosis and cirrhosis, and other liver damage-related conditions; the non-infectious hepatitis; the benign, malignant and unspecified liver neoplasms

Table 14-2 Liver Event Follow Up Requirements

| Criteria | Event type | Actions required | Follow-up monitoring |
|--|-----------------------|---|--|
| Potential Hy's Law case ^a | Medically significant | Discontinue the study drug immediately Hospitalize, if clinically appropriate Report to Novartis as an SAE Establish causality | ALT, AST, TBL, Alb, PT, ALP and γGT until resolution ^c (frequency at investigator discretion) |
| ALT or AST | | | |
| > 8 x ULN | Medically significant | Repeat LFT within 48 hours If elevation persists, discontinue the study drug immediately Hospitalize if clinically appropriate Report to Novartis as an SAE Establish causality | ALT, AST, TBL, Alb, PT, ALP and γGT until resolution ^c (frequency at investigator discretion) |

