2.1.1.2 Screening, baseline and post-baseline definitions

Screening period refers to the period starting from signing the informed consent until randomization or screening failure. Per protocol, subject informed consent must be obtained prior to performing any study related activity. The date of signing informed consent is the start date of screening period. Any assessment obtained during the screening period will be labeled screening assessment.

For efficacy analyses, baseline is the last available pre-dose assessment obtained at Visit 2. If the measurements at Visit 2 are missing then the measurements obtained at Visit 1 will be considered as the baseline. All assessments obtained after Visit 2, are considered as post-baseline.

For safety analyses, baseline is the last assessment obtained before the first dose of study treatment i.e. Secukinumab, is Visit 2. If the measurements at Visit 2 are missing then the measurement at Visit 1 will be considered as the baseline. All assessments obtained after the first dose of study treatment i.e. Secukinumab, are considered as post-baseline.

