2.9.1 Adverse events

Treatment emergent adverse events (events started after the first dose of secukinumab study treatment or events present prior to the first dose of secukinumab study treatment but increased in severity) will be summarized by preferred term up to 28 weeks after the first dose..

AEs will be summarized by presenting, for each treatment group, the number and percentage of patients having any AE, having an AE in each primary system organ class (SOC) and having each individual AE (preferred term).

Summaries will also be presented for AEs by severity and for secukinumab study treatment (with and without life-style intervention) related AEs. If a patient reported more than one adverse event with the same preferred term, the adverse event with the greatest severity will be presented. If a patient reported more than one adverse event within the same primary SOC, the patient will be counted only once with the greatest severity at the SOC level, where applicable. Furthermore, a listing of all adverse events, including SAE, will be provided. SAEs will be summarized.

Separate summaries will be provided for death, SAE, other significant AEs leading to secukinumab study treatment (with and without life-style intervention) discontinuation and AEs leading to dose adjustment (including secukinumab study treatment discontinuation).

Deaths occurring after signing of informed consent and prior to the start of the core study will be presented in the listing.

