2.9.2 Laboratory data

The summary of laboratory evaluations will be presented for three groups of laboratory tests (hematology, clinical chemistry and urinalysis). All the laboratory parameters and biomarkers with values below and above the limit of quantification (LOQ) will be reported as LOQ/2. Descriptive summary statistics for the change from Baseline to each study visit will be presented.

These descriptive summaries will be presented by test group, laboratory test and treatment group. Change from Baseline will only be summarized for patients with both Baseline and Post-Baseline assessments.

Change from baseline = post-baseline value – baseline value

For each parameter, the maximum change from Baseline within each study period will be analyzed analogously.

Below mentioned laboratory parameters will be descriptively summarized. Frequencies and percentages will be presented for patients with clinically notable laboratory value, for below mentioned selected lab parameters:

Clinically notable laboratory values

Liver Function and Related Variables

- ALT (SGPT): $> 3 \times$ Upper Limit of Normal (ULN)
- AST (SGOT): $> 3 \times$ ULN
- Total bilirubin: $> 1.5 \times$ ULN
- Alkaline phosphatase: $> 2 \times$ ULN

Renal Function and Electrolyte Variables

- Creatinine (serum): $> 1.5 \times$ ULN

Hematology Variables

- Hemoglobin: ≥ 20 g/dL decrease from baseline
- Platelet count: $<$ Lower Limit of Normal (LLN)
- White blood cell count: $< 0.8 \times$ LLN
- Neutrophils: $< 0.9 \times$ LLN
- Eosinophils: $> 1.1 \times$ ULN
- Lymphocytes: $> 1.1 \times$ ULN

Clinically significant abnormal laboratory values will also be summarized for the following parameters of the biomarker sub-study: Adiponectin, leptin, insulin, HOMA-IR, proinsulin, IL-6, TNF-alpha, M30 assay, NT-proBNP. Only patients participating in the biomarker sub-study will be included.

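### The clinically notable laboratory tables ignore baseline status for ten of 11 limits, so they cannot show how many patients crossed a limit on treatment

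*SAP*

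**What the plan says.** SAP 2.9.2 states: "Frequencies and percentages will be presented for patients with clinically notable laboratory value, for below mentioned selected lab parameters". The limits are ALT and AST above 3 x ULN, total bilirubin above 1.5 x ULN, alkaline phosphatase (ALP) above 2 x ULN, creatinine above 1.5 x ULN, platelets below LLN, WBC below 0.8 x LLN, neutrophils below 0.9 x LLN, and eosinophils and lymphocytes each above 1.1 x ULN. The eleventh is the only one tied to baseline: "Hemoglobin: ≥ 20 g/dL decrease from baseline".

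Nothing in the section requires a counted value to be new, worse than baseline or even post-baseline, and no shift table is planned. Baseline enters 2.9.2 otherwise only through summaries of change and maximum change in the continuous values, which is also all that protocol 9.5.2.2 promises.

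The list comes from protocol Appendix 1, introduced by "The following criteria will be used to define expanded limits and notable abnormalities of key laboratory tests", with no baseline condition for the same ten. Extension SAP 2.6.3 plans the same frequencies for the extension period, with haemoglobin judged against week 36.

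Two pieces that would support a baseline-aware count already exist. SAP 2.1.1.2 has a safety baseline: "For safety analyses, baseline is the last assessment obtained before the first dose of study treatment i.e. Secukinumab", with Visit 1 as fallback. For adverse events, SAP 2.9.1 includes pre-existing conditions only if they worsen: "events present prior to the first dose of secukinumab study treatment but increased in severity".

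**The concern.** A patient who enters with ALT above 3 x ULN and stays there meets the limit after baseline and is counted exactly like a patient who first crosses it in week 8. Restricting the count to post-baseline values does not help, because the persisting value still qualifies.

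Both arms receive secukinumab, so a safety reader will look at the within-arm percentages as well as the contrast. Randomisation balances carried-over cases between arms in expectation but does not remove them from either arm. A reader who wants to know how many patients developed a notable value on treatment cannot get that number from either planned table.

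**Working it through.** The plan states no figure on this point, so the check is a reading of the sections against each other, followed by an illustration.

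**1. Can an eligible patient be notable at entry?** Protocol 4.2 sets no numeric limit for ALT, AST, bilirubin, ALP, eosinophils or lymphocytes, so for these six it is possible under any reference range. For four others it depends on the laboratory's range, which the documents do not give:

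- creatinine: excluded above 2.0 mg/dl, flagged above 1.5 x ULN; overlap if ULN < 2.0/1.5 = 1.33 mg/dl
- platelets: excluded below 100,000/µl, flagged below LLN; overlap if LLN > 100,000/µl
- WBC: excluded below 2,500/µl, flagged below 0.8 x LLN; overlap if LLN > 2,500/0.8 = 3,125/µl
- neutrophils: excluded below 1,500/µl, flagged below 0.9 x LLN; overlap if LLN > 1,500/0.9 = 1,667/µl

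Protocol 1.1 links metabolic syndrome, an entry requirement, to non-alcoholic fatty liver disease, so raised liver values at entry are plausible. Non-numeric exclusions work the other way: criterion 15 (hepatic, renal, haematologic and other conditions, by investigator opinion), 16 (uncontrolled medical problems), 23 (hepatitis B or C) and 26 (alcohol abuse). They make entry abnormality less likely without ruling it out.

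**2. Does another planned output give the on-treatment count?**

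- Change and maximum-change summaries describe the group, not who crossed a limit.
- Protocol 7.1 turns laboratory values into adverse events if they are symptomatic, clinically significant or need therapy: "Clinically significant abnormal laboratory values or test results must be identified through a review of values outside of normal ranges/clinically notable ranges". Those reach the treatment-emergent tables, but the step depends on judgement.
- For higher liver values, cover is threshold-driven. Protocol Appendix 2 (Table 14-1, and "Table 14-2 Liver Event Follow Up Requirements") calls for SAE reporting of ALT or AST above 5 x ULN, ALP above 5 x ULN (in Table 14-2, if it persists) and bilirubin above 3 x ULN. SAP 2.9.1 summarises SAEs.
- For asymptomatic lower-band crossings (ALT/AST >3 to 5, ALP >2 to 5, bilirubin >1.5 to 3 x ULN) the label is adverse event of special interest. SAP 2.9.1 plans no separate summary of these, and protocol 7.3 handles liver abnormalities "irrespective of whether classified/reported as (S)AE".
- The six non-liver parameters have no threshold-driven cover.

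**3. Illustration (all rates assumed).** Let p be the share notable at entry, s the share of those with a notable value after baseline, and n the true onset rate among the rest.

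Rate shown = p·s + (1 − p)·n. Pre-existing share of the count = p·s / [p·s + (1 − p)·n].

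With the planned 380 per arm, n = 2% and s = 100%:

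| p | Rate shown | Patients counted | Pre-existing | Share |
|---|---|---|---|---|
| 0.5% | 2.49% | 9.46 | 1.90 | 20% |
| 1% | 2.98% | 11.32 | 3.80 | 34% |
| 2% | 3.96% | 15.05 | 7.60 | 51% |
| 3% | 4.94% | 18.77 | 11.40 | 61% |

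Less persistence lowers the share. At p = 1% it is 29% with s = 80% and 20% with s = 50%; at p = 3%, 55% and 44%. With p = 1% and s = 100%, it runs from 50% at n = 1% to 17% at n = 5%.

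**4. Between-arm difference.** With equal p and s in both arms, the difference shown is (1 − p) times the true one. A true 2.00 points appears as 0.99 x 2 = 1.98, 0.98 x 2 = 1.96 or 0.97 x 2 = 1.94 for p = 1%, 2% or 3%. Unequal persistence behaves differently. With p = 2%, n = 2% in both arms, and s = 100% against 50%, the table shows 0.02 + 0.98 x 0.02 = 3.96% against 0.01 + 0.98 x 0.02 = 2.96%, one point from resolution alone.

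**5. Proposed count.** At p = 1% and n = 2%, 380 x 0.99 = 376.2 patients are at risk and 7.52 cross: 7.52/376.2 = 2.00%, the true onset.

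**The case against.** The strongest reply is that nothing here is an error. The tables count patients beyond absolute alert ranges, are descriptive, and are not labelled treatment-emergent; neither the protocol nor the SAP promises an onset count. That stands, and it is why this is an improvement and not a correction.

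Second, serious liver deterioration does not go unseen. A patient going from ALT 3.1x to 10x ULN falls in a band for which Table 14-2 calls for SAE reporting, and so should reach the SAE summary. A reader might infer that new liver signals would be missed altogether; the documents do not support that for the higher bands. Cover stays incomplete for asymptomatic lower-band crossings and for the non-liver parameters.

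Third, the arm comparison is the randomised question, and both arms get the same approved drug and dose. A reader might infer that the comparison is biased. With similar persistence it is only slightly diluted. The unequal-persistence case is conceivable, since protocol 1.1 cites weight loss reducing liver-tissue inflammation, but the documents give no resolution rates to show that it would occur.

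Fourth, the percentages in the illustration are algebra on assumed inputs. That also stands: 20% to 61% is not an estimate for this trial.

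**Conclusion.** The point holds as a cheap improvement. Ten of 11 limits in core SAP 2.9.2, and the same ten in extension SAP 2.6.3, are applied without regard to baseline. The tables are therefore valid counts of patients with a notable value but cannot show how many crossed a limit on treatment, and no other planned output gives that number.

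The size is unknown: it depends on entry prevalence, persistence and reference ranges, none of which the documents report. The consequence is limited, because no test or stated objective uses the tables and the between-arm difference is little changed if persistence is similar. The 20 g/dL haemoglobin threshold is a separate issue and adds no weight here.

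**What to change.** In SAP 2.9.2, for the ten ULN/LLN-based limits:

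- Report by arm the patients with at least one post-baseline notable value among those not notable at the safety baseline of 2.1.1.2 who have a post-baseline value, with that group as denominator.
- Add a shift table by arm from baseline to worst post-baseline value, with a row for missing baseline, so that worsening in patients already notable stays visible.
- For liver tests use the Table 14-2 bands: ALT/AST up to 3, >3 to 5, >5 to 8 and >8 x ULN; ALP up to 2, >2 to 5 and >5; bilirubin up to 1.5, >1.5 to 3 and >3.
- For creatinine, platelets, WBC, neutrophils, eosinophils and lymphocytes, a notable/not-notable split is enough, plus a listing of patients notable at baseline.

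In extension SAP 2.6.3, show baseline status in the same way. Leave haemoglobin relative to its reference value and deal with its threshold separately.

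The cost is SAP wording, one programming condition and one shift table per document. Protocol Table 6-1 already schedules routine laboratory tests at Visits 1 and 2, so no new data are needed. The downsides are lower headline counts and some sparse cells.

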14. Active ongoing inflammatory diseases other than psoriasis and psoriatic arthritis (PsA) that might confound the evaluation of the benefit of Secukinumab therapy.

15. Underlying conditions (including, but not limited to metabolic, hematologic, renal, hepatic, pulmonary, neurologic, endocrine, cardiac, infectious or gastrointestinal) which in the opinion of the investigator significantly immunocompromises the subject and/or places the subject at unacceptable risk for receiving an immunomodulatory therapy.
16. Significant, progressive or uncontrolled medical problems at baseline which according to the opinion of the Investigator render the subject unsuitable for the trial - also in regard to participation in the lifestyle intervention - or put the subject at increased risk when participating in the trial (e.g. broken leg, congestive heart failure NYHA III/IV, uncontrolled hypertension with systolic ≥ 160 mmHg and/or diastolic ≥ 95 mmHg, severe uncontrolled asthma)
17. Medical history of myocardial infarction or angina pectoris
18. Any medical or psychiatric condition which, in the Investigator's opinion, would preclude the participant from adhering to the protocol or completing the study per protocol.
19. Serum creatinine level exceeding 2.0 mg/dl (176.8 $\mu\text{mol/L}$) at screening
20. Total white blood cell (WBC) count $< 2,500/\mu\text{l}$, or platelets $< 100,000/\mu\text{l}$ or neutrophils $< 1,500/\mu\text{l}$ or hemoglobin < 8.5 g/dl at screening.
21. Active systemic infections during the last two weeks (exception: common cold) prior to baseline (visit 2) or any infection that reoccurs on a regular basis.
22. History of an ongoing, chronic or recurrent infectious disease, or evidence of tuberculosis infection as defined by a positive QuantiFERON TB-Gold test (QFT) at screening. Subjects with a positive or indeterminate QFT test may participate in the study if full tuberculosis work up (according to local practice/guidelines) was completed within 12 weeks prior to visit 2 and establishes conclusively that the subject has no evidence of active tuberculosis. If presence of latent tuberculosis is established, then appropriate treatment must have been initiated at least 4 weeks prior to baseline (visit 2) and maintained according to local guidelines.
23. Past medical history record or current infection with HIV, hepatitis B or hepatitis C prior to baseline (visit 2).

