2.6.3 Laboratory data

The summary of laboratory evaluations will be presented for three groups of laboratory tests (hematology, clinical chemistry, and urinalysis) separately, for extension period, based on the FAS. Data for hematology, clinical chemistry, and urinalysis will be listed separately. All the laboratory parameters and markers with values below Limit of quantification (LOQ) will be reported as LOQ/2. Descriptive summary statistics for each study visit will be presented.

These descriptive summaries will be presented by laboratory test group, laboratory test. An additional summary table will be reported for the patients chosen for being administered secukinumab by the physician.

The below-mentioned laboratory parameters will be descriptively summarized. Frequencies and percentages will be presented for patients with clinically notable laboratory values, for the below-mentioned selected lab parameters:

Clinically notable laboratory values

Liver Function and Related Variables

- ALT (SGPT): $> 3 \times$ Upper Limit of Normal (ULN)
- AST (SGOT): $> 3 \times$ ULN
- Total bilirubin: $> 1.5 \times$ ULN
- Alkaline phosphatase: $> 2 \times$ ULN

Renal Function and Electrolyte Variables

- Creatinine (serum): $> 1.5 \times$ ULN

Hematology Variables

- Hemoglobin: ≥ 20 g/dL decrease from week 36
- Platelet count: $<$ Lower Limit of Normal (LLN)
- White blood cell count: $< 0.8 \times$ LLN
- Neutrophils: $< 0.9 \times$ LLN
- Eosinophils: $> 1.1 \times$ ULN
- Lymphocytes: $> 1.1 \times$ ULN

Clinically significant abnormal laboratory values will also be summarized based on the FAS.

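### The haemoglobin criterion for a clinically notable value, a fall of at least 20 g/dL, cannot be met by any baseline below 20 g/dL, so its table row will show zero whatever happens

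*SAP*

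**What the plan says.** Protocol section 13 (Appendix 1) introduces its list with "The following criteria will be used to define expanded limits and notable abnormalities of key laboratory tests". The haemoglobin entry in that list is a decrease of 20 g/dL or more from baseline. Protocol 7.1 directs investigators there: "Alert ranges for laboratory and other test abnormalities are included in Appendix 1".

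Core SAP 2.9.2 carries the list over, with the haemoglobin entry, after a greater-than-or-equal sign, reading "20 g/dL decrease from baseline". It commits to an output based on the list: "Frequencies and percentages will be presented for patients with clinically notable laboratory value". Extension SAP 2.6.3 repeats both the list and the commitment, with the reference point moved: "20 g/dL decrease from week 36". The biomarker sub-study SAP does not contain the criterion.

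For eligibility, Protocol 4.2 (criterion 20) excludes patients with "hemoglobin < 8.5 g/dl at screening". Core SAP 5.4 repeats that limit under deviation EXCL20.

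**The concern.** A fall of 20 g/dL is out of scale with the haemoglobin limit of 8.5 g/dL that the same documents use for entry. If the criterion cannot be met, the row reports zero by construction, and a reader cannot tell that zero from a true absence of notable falls.

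Haemoglobin has no second criterion in the list as a backstop. It is the only entry defined by an absolute change in a measured unit. Every other entry is set at or as a multiple of a normal limit (for example platelets below the lower limit of normal, or creatinine above 1.5 times the upper limit), so none of the others is exposed to an error of this kind. The same figure is also one of the alert ranges offered to investigators.

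**Working it through.** **Inputs**
- Threshold T = 20 g/dL, as a fall (Protocol Appendix 1; core SAP 2.9.2; extension SAP 2.6.3).
- Definition of change (core SAP 2.9.2): "Change from baseline = post-baseline value" minus the baseline value.
- Entry limit: excluded below 8.5 g/dL at screening (Protocol 4.2). No upper limit is stated.
- Assumption, not in the documents: adult baselines lie roughly between 8.5 and 18 g/dL. Higher values are shown as well, so that the conclusion does not depend on this range.

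The threshold is stated without a derivation, so there is no figure of the plan's own to reproduce.

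**Step 1: largest possible fall.** Haemoglobin cannot be below 0, so the largest fall is baseline − 0 = baseline. The criterion can be met only if baseline ≥ 20 g/dL.

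**Step 2: value needed to be counted.** Required later value ≤ baseline − 20.

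| Baseline (g/dL) | Later value needed (g/dL) | Possible? |
|---|---|---|
| 8.5 | −11.5 | no |
| 10 | −10 | no |
| 12 | −8 | no |
| 14 | −6 | no |
| 16 | −4 | no |
| 18 | −2 | no |
| 19.9 | −0.1 | no |
| 20 | 0 | only at zero |
| 22 | 2 | arithmetically, after a fall of 20/22 = 91% |

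Patients kept in the analysis despite a screening value below 8.5 g/dL are further still from meeting the criterion. For the extension period the same arithmetic applies with the week 36 value in place of baseline.

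**Step 3: could this be a text-reading artefact?** The figure is 20 in all three places. Decimals in the same lists (1.5, 0.8, 0.9, 1.1) and the 8.5 g/dL entry limit were read correctly. No other section corrects the entry.

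**Step 4: scale of the mismatch.** 20 g/L ÷ 10 = 2.0 g/dL. On that scale a baseline of 14 g/dL would be counted at 12 g/dL or below, a fall of 2/14 = 14.3%. This shows only why a unit slip is a natural guess. A dropped decimal point would print the same figure, and the documents do not settle which occurred, if either.

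**The case against.** The strongest reply is that little is lost.

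- **Other core-study summaries.** Core SAP 2.9.2 and Protocol 9.5.2.2 require change from baseline at each visit and maximum change within each study period for haematology, and haemoglobin is in that panel (Protocol 6.5.4.1).
- **Other routes for investigators.** Under Protocol 7.1 significant results are also found from values outside normal ranges, marked changes from baseline or the previous visit, and values untypical for the disease. Protocol 6.5.4 refers sites to the Laboratory Manual for reference ranges and out-of-range notification. No predefined action depends on a haemoglobin value.
- **Limited relevance to the comparison.** Both arms receive the same drug, and the risks named in Protocol 3.6 do not include anaemia.

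All of this stands, and it limits the severity. It does not rescue the criterion. Summaries of change do not count affected patients, which is what this table is for. The cover is also thinner in the extension period, where section 2.6.3 promises per-visit descriptive statistics, listings and a summary of clinically significant abnormal values, but no change or maximum-change summary.

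Three stronger readings are tempting, and the documents do not support them:
- A reader might infer that falls in haemoglobin would go unseen in the trial. The other routes above contradict that.
- A reader might infer that the zero row will be presented as reassurance. The documents do not say how it will be interpreted.
- A reader might infer that the unit is certainly wrong and should read g/L. The number could equally be the error.

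**Conclusion.** The criterion is wrong as written. For any starting value below 20 g/dL it is arithmetically impossible. Above that it is unattainable in practice, a judgement that rests on general knowledge because the documents set no upper haemoglobin limit. Under the assumed range of 8.5 to 18 g/dL the required value is always negative (−11.5 to −2 g/dL), so the expected count is zero in both arms.

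The damage is one uninformative row in each of the two notable-value tables (core and extension) and one void alert range in Appendix 1. The primary endpoint, sample size, hypothesis test and eligibility are untouched. This is a should-fix.

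**What to change.** The sponsor's safety lead should confirm both the intended number and the intended unit. No value is proposed here. The confirmed criterion, checked to be attainable, should then replace the present entry in Protocol Appendix 1, core SAP 2.9.2 and extension SAP 2.6.3. The extension SAP should keep its week 36 reference point only if that is intended. The notable-value tables should be produced with the corrected criterion.

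The cost is one line in each of three documents and one derivation in the table program. No new data are needed, because haemoglobin is already collected with the routine haematology panel. The extension SAP's document history dates its addendum after final database lock, so a correction made now should be recorded as a post-lock change. The documents do not show whether the tables have already been run.
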